## 6.8 Timing of Temporary Discontinuation Relative to Assessment of Primary and Secondary Outcomes

If a temporary intervention discontinuation occurs near the time of the scheduled Month 6 or Month 12 clinic assessment, the acceptable window within which to complete this visit may be expanded by up to 6 weeks if this would allow participants to resume the intervention at the prescribed dose for at least 3 weeks prior to the assessment. If longer delays are required to meet this goal, the assessment visit will be completed according to the original schedule. The decision to postpone an assessment visit will be made by the Intervention Oversight Team, in consultation with the site PI and the ADCS, on a case-by-case basis.

## 6.9 Blinding

The Study Clinician and the Clinic YMCA Liaison will be unblinded to intervention group assignment; all other clinic staff will remain blinded. The Study Clinician will be responsible for reviewing and following up on all AEs. The Clinic YMCA Liaison serves as the primary interface between the participating YMCA and the clinic, and thus will be exposed to intervention-specific details for participants. The description of TEAEs may relate to physical activities completed as part of the assigned intervention. Disclosure of randomization assignment will occur in the clinic by either the Clinic YMCA Liaison or the Study Clinician.

It will be critically important that the clinic staff member(s) who administer the cognitive and functional assessment instruments to participants (referred to as 'Raters') remain blinded. Unblinded staff will not discuss any details about a participant's intervention or progress with the Rater, and the Rater will not have access to any intervention-related data, including AEs, supervised exercise adherence data, or participant Physical Activity Logs. Participants will be instructed by the Clinic YMCA Liaison at the start of each clinic visit to refrain from sharing any information about their assigned intervention with the Rater or other clinic staff (other than the Study Clinician). Signs will be clearly posted in all testing rooms to remind participants to not

share information about their assigned exercise program, and Raters will also remind participants to keep this information to themselves at frequent intervals. These procedures to ensure that the Rater remains blinded to intervention assignment have been used with success in other randomized clinical trials of aerobic exercise in non-demented older adults.

The Wake Forest team and the Y-USA will remain unblinded so that they may assist the Trainers, Y-PMs, and Clinic YMCA Liaisons with intervention-specific challenges as they arise. The Project Directors will remain blinded to primary and secondary outcomes by intervention group assignment.

### **6.10 Breaking the Blind**

Decisions regarding breaking the blind for clinic personnel other than the Clinic YMCA Liaison and Study Clinician must be made in consultation with the PDs and the ADCS Medical Director. If the blind is broken for other clinic staff members in any instance, the site PI must document the following information on a Blind Break Notification Form for the participant: date, personnel exposed, and why/how blind was broken. An alternate plan for assessment of primary outcomes at future clinic visits may be requested by the PDs and the ADCS.

### **6.11 Concomitant AD Medications**

Stable use of memantine or cholinesterase inhibitors at study entry will be permitted (3 or more months at a consistent dose with no plans to modify). Participants who start AD medications after enrollment will be permitted to continue in the study.

## **7.0 STUDY POPULATION**

A total of 300 adults diagnosed with test scores and clinical ratings consistent with amnesic MCI will be enrolled into EXERT. To determine eligibility, all participants will undergo cognitive assessment, physical and neurological examination, electrocardiogram (ECG), clinical/safety laboratory assessment, and interviews of the participant and study partner.

### **7.1 Inclusion Criteria**

1. Age between 65 and 89 years old, inclusive
2. MMSE:  $\geq 24$  for participants with 13 or more years of education;  $\geq 22$  for participants with 12 or fewer years of education
3. Global CDR score of 0.5 with a memory score of at least 0.5
4. Profile of test scores and clinical ratings is consistent with amnesic mild cognitive impairment
5. Speaks English fluently
6. Visual and auditory acuity adequate for cognitive testing
7. Completed at least 6 years of formal education or work history sufficient to exclude mental retardation

8. Has an informant who knows the participant well, has regular contact, and is available to accompany the participant to clinic visits or complete study partner assessments remotely.
9. Sedentary or underactive, determined by responses to the staff-administered EXERT Telephone Assessment of Physical Activity (TAPA) survey
10. Willing to be randomized to either intervention group and to complete the assigned activities as specified for 18 months
11. Willing and able to reliably travel to the identified YMCA, 4 times per week for 18 months
12. Ability to safely participate in either intervention and complete the 400 m Walk Test within 15 min without sitting or use of any assistance
13. Plans to reside in the area for at least 18 months
14. For planned travel, total time away must be no more than 2 months over the course of the study, and no more than 1 month at any one time; participants must be willing to continue the assigned exercise program if travelling out of the area for more than 1 week
15. In overall good general health with no disease or planned surgery that could interfere with study participation
16. Modified Hachinski  $\leq 4$
17. Stable use of cholinesterase inhibitors, memantine, vitamin E, estrogens, aspirin (81-300 mg daily), beta-blockers, or cholesterol-lowering agents for 12 weeks prior to screening (important for biomarker analyses)
18. Stable use of antidepressants lacking significant anticholinergic side effects for 4 weeks prior to screening as long as the participant does not meet DSM V criteria for major depression currently or in the last 12 months; GDS scores are to be used to inform clinical decisions but there is no specified cut-off score for inclusion
19. When applicable, willing to complete 4-week washout of psychoactive medications, including disallowed antidepressants, neuroleptics, chronic anxiolytics or sedative hypnotics, and willing to avoid these medications for the duration of the trial
20. Able to complete all baseline assessments

## 7.2 Exclusion Criteria

1. Any significant neurologic disease, other than MCI, including any form of dementia, Parkinson's disease, Huntington's disease, normal pressure hydrocephalus, brain tumor, progressive supranuclear palsy, seizure disorder, subdural hematoma, multiple sclerosis, or history of significant head trauma with persistent neurologic sequelae or known structural brain abnormalities
2. Sensory or musculoskeletal impairment sufficient to preclude successful and safe completion of the intervention or assessment protocols; must be able to walk safely and unassisted on a treadmill
3. Contraindications for MRI studies, including claustrophobia, metal (ferromagnetic) implants, or cardiac pacemaker
4. Brain MRI at screening shows evidence of infection, infarction, or other clinically significant focal lesions, including multiple lacunes in prefrontal or critical memory regions; inconclusive findings may be subject to review by the ADCS Imaging Core

5. History of major depression or bipolar disorder (DSM V criteria), psychotic features, agitation or behavioral problems within the last 12 months
6. History of schizophrenia, as per DSM V criteria
7. History of alcohol or substance abuse or dependence within the past 2 years, as per DSM V criteria
8. Currently consumes more than 3 alcoholic drinks per day
9. Clinically significant or unstable medical condition, including uncontrolled hypertension or significant cardiac, pulmonary, hematologic, renal, hepatic, gastrointestinal, endocrine, metabolic or other systemic disease in the opinion of clinic medical personnel that may put the participant at increased risk, influence the results or compromise the participant's ability to participate in the study (treated atrial fibrillation for more than 1 year or occasional premature ventricular contractions on ECG are not exclusions)
10. History in the last 6 months of myocardial infarction, coronary artery angioplasty, bypass grafting, or STENT placement
11. History in the last 3 months of transient ischemic attack or small vessel stroke (if more than 3 months, small vessel stroke with no residual effects are permitted)
12. Expected joint replacement surgery within the next 18 months
13. History within the last 5 years of a primary or recurrent malignant disease with the exception of non-melanoma skin cancers, resected cutaneous squamous cell carcinoma in situ, basal cell carcinoma, cervical carcinoma in situ, or in situ prostate cancer with normal prostate-specific antigen posttreatment
14. Hemoglobin A1c >7.0
15. Clinically significant abnormalities in screening laboratory blood tests: low B12 is exclusionary, unless follow-up labs (homocysteine [HCY] and methylmalonic acid [MMA]) indicate that it is not physiologically significant
16. Current or past use of insulin to treat type 2 diabetes (other diabetes medications are acceptable if hemoglobin A1c  $\leq$ 7)
17. Current use (within 60 days of screening) of psychoactive medications including tricyclic antidepressants, antipsychotics, mood-stabilizing psychotropic agents (e.g. lithium salts), psychostimulants, opiate analgesics, antiparkinsonian medications, anticonvulsant medications (except gabapentin and pregabalin for non-seizure indications), systemic corticosteroids, or medications with significant central anticholinergic activity. Limited use of antipsychotics (quetiapine  $\leq$  50mg/day or risperidone  $\leq$  0.5mg/day), and non-chronic use of opiate analgesics on an as needed basis is permitted; such medications must be avoided for 8 hours before clinic assessments
18. Chronic use of anxiolytics or sedative hypnotics except as follows: use of benzodiazepines for treatment on an as-needed basis for insomnia or daily dosing of anxiolytics is permitted; medications must be avoided for 8 hours before clinic assessments
19. Previous or current treatment involving active immunization against amyloid
20. Previous treatment with approved or investigational agents with anti-amyloid properties or passive immunization against amyloid are prohibited 12 months prior to screening and for the duration of the trial; treatment with other investigational agents are prohibited 3 months prior to screening and for the duration of the trial
21. For LP, current use of anticoagulants such as Coumadin, Plavix, or high dose Vitamin E

22. For LP, current blood clotting or bleeding disorder, or significantly abnormal prothrombin time (PT) or partial thromboplastin time (PTT) at screening
23. For LP, presence of physical distortions due to spinal surgery, severe degenerative joint disease or deformity, or obesity that could interfere with CSF collection (as per investigator judgment)
24. Participants whom the PI deems otherwise ineligible

### **7.3 Recruitment and Retention Strategies**

A recruitment plan will be developed in coordination with the ADCS and its study partners. The plan will include national media releases and EXERT-specific study materials that can be used by the clinics to recruit participants upon receipt of local IRB approval to do so. Multiple strategies will be used to promote high rates of retention, including twice weekly meetings with the Trainer, opportunities to participate in group exercise activities, and by providing tangible reinforcers as participants advance through the study (e.g., quilts, T-shirts, exercise accomplishment reports).

### **7.4 Inclusion of Women and Minorities**

No subject will be excluded for reasons of sex, race, or ethnic group. There are currently no studies that definitively support or negate differences in response to aerobic exercise within these subgroups. Consistent with the aims of the ADCS Minority Recruitment Core, EXERT will target a minimum of 20% racial/ethnic minority representation in the sample of 300 older adults.

## **8.0 STUDY TIMELINE**

Study participation will include up to 6 weeks between Screening II (Visit 1) and Baseline (Visit 2), 12 months of supervised exercise at a local YMCA facility, and 6 months of unsupervised exercise at the YMCA.

## **9.0 DESCRIPTION OF STUDY VISITS**

The schedule of events is provided in **Appendix 1**.

### **9.1 Screening I (Visit 0)**

Prior to the in-person screening evaluation, the investigator will identify potential participants through routine clinical contact or an additional screening process. Prospective participants will have a subjective memory complaint and/or demonstrate memory impairments during screening, will be considered 'sedentary' as assessed by the EXERT TAPA, will meet all other inclusion/exclusion criteria, and will agree to be randomized to either the SBR or AX group. Study candidates may provide verbal consent over the telephone to complete the EXERT TAPA and other screening questions regarding demographics, medical history, and medications to assess eligibility for continued screening, if permitted by the local IRB. Study candidates and

their collaterals will not be considered as EXERT participants until the core study consent form is signed at an in-person screening visit.

## 9.2 Screening II (Visit 1)

This assessment will determine eligibility to enroll in EXERT, and may be conducted over multiple days. Potential participants and their study partners must sign an informed consent form (ICF) and Health Insurance Portability and Accountability Act (HIPAA) authorization prior to administration of any procedures for this assessment. Screening II procedures will include the following:

- ICF/HIPAA: participant and study partner
- Review of inclusion/exclusion criteria (includes review of EXERT TAPA responses)
- Demographics review
- Medical history
- Medication review
- Brief physical examination, vital signs, weight, height
- Brief neurological examination
- Modified Hachinski
- Blood collection for ApoE genotyping, and DNA banking
- Blood collection for clinical labs
- 12-lead resting ECG
- Cognitive assessment
  - 3MSE/MMSE
  - Logical Memory I and II
  - Auditory Verbal Learning Test (AVLT)
- Behavioral/functional assessment
  - CDR
  - Cognitive Change Index (self-administered)
  - GDS (self-administered)
- 400 m Walk Test
- Brain MRI
  - For participants meeting all other eligibility criteria (as determined by site investigator)
  - Participants may be excluded from enrollment if safety concerns are identified
  - At approved sites, protocol will include EXERT fMRI sequences
- Dispense ActiGraph Link for actigraphy data collection
  - Dispense following completion of screening procedures to participants who meet eligibility criteria and thus are at high probability of randomization
  - Device should be placed on the participant's non-dominant wrist at the clinic to initiate the recording period
  - Device should continuously remain on the participant's wrist for the duration of the 10-day recording period

- Retrieve ActiGraph Link device 10 days later during a baseline visit or by mail (with a reminder call on Day 10), and upload data
- Data collection should be completed prior to randomization

The participant will be permitted to proceed to the baseline visit if all inclusion/exclusion criteria are met, results from all screening procedures are reviewed, and eligibility have been approved by the site investigator. The PDs, in consultation with the ADCS Medical Director, must approve any exceptions or questions regarding possible exclusionary medications, medical conditions, or laboratory tests. In addition, the PDs must approve any exceptions to cognitive eligibility criteria in cases where there is compelling evidence for MCI but not all cognitive eligibility criteria are met.

The baseline visit should be scheduled within 6 weeks of Screening II. A re-screen is allowed in the event of a screen failure, but must occur more than 90 days later. If the baseline visit is scheduled more than 6 weeks from Screening II (i.e., out-of-window), approval to proceed to the baseline visit must be obtained from the ADCS and a rescreen may be required.

### 9.3 Baseline (Visit 2)

Baseline procedures may be completed over multiple days, but all assessments should be completed within 14 days, with the condition that cognitive and behavioral assessments should not be administered while participants are fasting. Cognitive testing conducted after an LP must be administered at least 48 hours following the procedure. All baseline assessments must be completed before randomization and start of exercise, and include:

- Review of inclusion and exclusion criteria
- Medication review
- Vital signs, weight
- Fasting blood collection for banking
- AE query
- Cognitive assessment
  - Primary outcomes assessment (administer the following tests before administering other cognitive/behavioral instruments)
    - ✓ ADAS-Cog13
    - ✓ Trail-Making Test
    - ✓ DSST
    - ✓ Category and Letter Word Fluency
  - Secondary outcomes assessment (iPad computer tests)
    - ✓ Cogstate: Detection task (DET), Identification task (IDN), One Card Learning (OCL), One Back task (OBK), Groton Maze Learning Test (GMLT), Face Name Associative Memory (FNAME), Behavioral Pattern Separation of Objects (BPSO)
    - ✓ NIH Toolbox: Flanker, Dimensional Change Card Sort (DCCS)
- Behavioral/functional and other outcomes assessments

- Staff-administered questionnaires
  - ✓ ADCS-ADL-MCI
  - ✓ BRIEF-A
  - ✓ NPI
- Self-administered questionnaires
  - ✓ By participant
    - SF-36
    - EQ5D
    - Research Satisfaction Survey
  - ✓ By study partner
    - Study Partner Self-Assessment Questionnaire (SF-36, Pittsburgh Sleep Quality Index, Insomnia Severity Index, questions regarding healthcare utilization)
    - EQ5D (as it relates to participant)
- LP
  - For participants who agree to the LP
  - Follow-up telephone call by staff within 24 hours to query AEs
- Randomization
  - Eligible participants will be randomized to either the SBR or AX group centrally by the ADCS using a real-time web-based randomization system
  - Designated unblinded clinic staff member will disclose this assignment to the participant, in person, when all baseline assessments have been completed
  - Participants will be provided with a packet of materials describing their assigned intervention, their responsibilities to the study, and what the study will provide for them. At a YMCA appointment, Trainers will provide participants with a HR monitor, the first Physical Activity Log, and the appropriate Activity Resource Guide.
  - Participants will be instructed to maintain their regular diet and other activities for the duration of the study
  - At time of disclosure, and once the provided materials have been carefully reviewed with the participant, the participant will be asked to sign a document indicating his/her willingness to complete the assigned programs as instructed, for the duration of the 18-month trial
  - Participants will be provided with the name and contact information of the site Y-PM who will follow-up within 3 weekdays to schedule the first appointment at the YMCA, which should be completed within 2 weeks of the last baseline visit
  - Participants will be instructed to withhold all information about intervention group assignment from all other clinic staff members throughout study participation; the importance of keeping this 'secret' will be emphasized and discussed
- At Site PI discretion, an optional letter can be provided to notify the participant's primary care physician of participant enrollment in the study.

Beginning in Month 1, Clinic YMCA Liaison will complete a monthly telephone call to query AEs, obtain medication updates, provide encouragement, and problem-solve challenges to continued participation.

#### 9.4 Month 6 (Visit 3)

The Month 6 assessment should be completed 6 months (+/- 2 weeks) from the participant's first appointment at the YMCA that initiated the intervention. Participants will be asked to bring their HR monitor to the appointment and to refrain from exercise for 24 hours prior to cognitive testing, which should not be completed while participants are fasting. Month 6 procedures include:

- Fasting blood collection for banking
- Medication review
- Brief physical exam, vital signs, weight
- Brief neurological exam
- AE query
- Briefly review adherence with participant using report provided through EDC and entries in the Physical Activity Logs (adherence will be regularly monitored by the YMCA Trainer, the Y-PM and the Intervention Oversight Team as well)
- Cognitive assessment
  - Primary outcomes assessment (administer the following tests before administering other cognitive/behavioral instruments)
    - ✓ ADAS-Cog13
    - ✓ Trail-Making Test
    - ✓ DSST
    - ✓ Category and Letter Word Fluency
  - Secondary outcomes assessment (iPad computer tests)
    - ✓ Cogstate: DET, IDN, OCL, OBK, GMLT, FNAME, BPSO
    - ✓ NIH Toolbox: Flanker, DCCS
- Behavioral/functional and other outcomes assessments
  - Staff-administered questionnaires
    - ✓ CDR
    - ✓ ADCS-ADL-MCI
    - ✓ BRIEF-A
    - ✓ NPI
  - Self-administered questionnaires
    - ✓ By participant
      - Cognitive Change Index
      - SF-36
      - EQ5D
      - Research Satisfaction Survey
    - ✓ By study partner

- Study Partner Self-Assessment Questionnaire (SF-36, Pittsburgh Sleep Quality Index, Insomnia Severity Index)
- EQ5D (as it relates to participant)
- 400 m Walk Test
- Dispense ActiGraph Link for actigraphy data collection
  - Place device on the participant's non-dominant wrist to initiate recording period
  - Device should continuously remain on the participant's wrist for the duration of the 10-day recording period
  - Retrieve device from participant 10 days later by return mail (with a reminder call on Day 10), and upload data when device is received
- Replace battery in HR monitor
- Provide participant with 6-month supply of Physical Activity Logs

The Clinic YMCA Liaison will continue to complete monthly telephone calls to query AEs, obtain medication updates, provide encouragement, and problem-solve challenges to continued participation.

## 9.5 Month 12 (Visit 4) / or Early Termination

The Month 12 assessment will provide the primary endpoints to evaluate trial efficacy, and should be completed 12 months (+/- 2 weeks) from the participant's first appointment at the YMCA that initiated the intervention. The following procedures may be completed over multiple days, but within a 7-day window. Participants will be instructed to bring their HR monitor to the appointment and to refrain from exercise for 24 hours prior to cognitive testing, fMRI (for approved sites), and the LP. Cognitive testing should not be completed while participants are fasting, and if conducted after an LP, testing must be administered at least 48 hours following the procedure. Month 12 procedures include:

- Fasting blood collection for clinical labs
- Fasting blood collection for banking
- Medication review
- Brief physical exam, vital signs, weight
- Brief neurological exam
- AE query
- Briefly review adherence with participant using report provided through EDC and entries in the Physical Activity Logs (adherence will be regularly monitored by the YMCA Trainer, the Y-PM and the Intervention Oversight Team as well)
- Cognitive assessment
  - Primary outcomes assessment (administer the following tests before administering other cognitive/behavioral instruments)
    - ✓ ADAS-Cog13
    - ✓ Trail-Making Test
    - ✓ DSST
    - ✓ Category and Letter Word Fluency

- Secondary outcomes assessment
  - ✓ 3MSE/MMSE
  - ✓ iPad computer tests
    - Cogstate: DET, IDN, OCL, OBK, GMLT, FNAME, BPSO
    - NIH Toolbox: Flanker, DCCS
- Behavioral/functional and other outcomes assessments
  - Staff-administered questionnaires
    - ✓ CDR
    - ✓ ADCS-ADL-MCI
    - ✓ BRIEF-A
    - ✓ NPI
  - Self-administered questionnaires
    - ✓ By participant
      - Cognitive Change Index
      - SF-36
      - EQ5D
      - Research Satisfaction Survey
    - ✓ By study partner
      - Study Partner Self-Assessment Questionnaire (SF-36, Pittsburgh Sleep Quality Index, Insomnia Severity Index)
      - EQ5D (as it relates to participant)
- 400 m Walk Test
- Brain MRI
  - At approved sites, protocol will include fMRI sequences
- LP
  - CSF may be collected at this visit, even if not successfully collected at Baseline
  - Follow-up telephone call by staff within 24 hours to query AEs
- Dispense ActiGraph Link for actigraphy data collection
  - Place on the participant's non-dominant wrist to initiate recording period
  - Device should continuously remain on the participant's wrist for the duration of the 10-day recording period
  - Retrieve device from participant 10 days later by return mail (with a reminder call on Day 10), and upload data when device is received
- Replace battery in HR monitor
- Provide participant with 6-month supply of Physical Activity Logs
- Site PI and Raters to complete Treatment Blinding Questionnaire

All participants will transition to unsupervised exercise during the last 6 months of the study. Participants will be instructed to continue their assigned intervention at the specified frequency, duration, and intensity, and to continue to track their exercise using their Physical Activity Log. During this phase of the study, the Clinic YMCA Liaison will continue to contact participants by telephone, once per month to query AEs, obtain medication updates, provide encouragement, and problem-solve challenges to continued participation.

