### 12.2.2 Blood Collection for Biomarker Analyses and Banking

Blood will be collected to extract plasma and peripheral blood mononuclear cells (PBMCs) in the morning after a minimum 10-hour overnight fast, and shipped to the ADCS Biomarker Core at UCSD for banking and analysis.

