### 12.2.3 CSF Collection for Biomarker Analyses and Banking

It is expected that most participants will receive LPs pre- and post-treatment. Coagulation and platelets will be examined in blood before an LP is performed. All CSF samples will be collected after an overnight fast. Participants who are taking anticoagulants, warfarin (Coumadin) and dabigatran (Pradaxa) should not be screened for an LP, as these are prohibited medications. Based on clinician judgment and depending on the clinical indication, it may be suitable to discontinue participants from their anti-platelet agent (e.g., aspirin, Plavix, NSAIDs) for 5-7 days prior to the LP and until at least 24 hours after the procedure. It is not required that participants be discontinued from their anti-platelet agent in order to screen and enroll in EXERT.

The baseline LP must be conducted prior to randomization. At Month 12, the LP should be performed after the MRI or at least 72 hours before the MRI, and at least 24 hours after the last bout of exercise.

A total of 20 ml of CSF will be collected during each LP. To clear any blood from minor trauma associated with needle insertion, the first 1-2 mL of CSF are discarded (or more if needed). Collected CSF will be aliquoted into sterile microtubes. Approximately 2 mL of CSF or volume per local laboratory requirements will be sent at ambient temperature to the local laboratory for protein, glucose and cell count. The remaining CSF will be shipped to the ADCS Biomarker Core at UCSD for storage and analysis.

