5.2 Secondary Aims

- 5.2.1 Key second aim:** to test the hypothesis that 12 months of aerobic exercise, relative to the control, improves scores on the primary outcome (ADAS-Cog-Exec) in the subset of participants who had the opportunity to complete a full 12 months of the study (i.e., 12 months of exercise and the 12 Month outcomes assessment) before the COVID-19 pandemic affected trial conduct.
- 5.2.2** To test whether 12 months of supervised aerobic exercise, relative to the control, improves executive function and episodic memory measured by domain-specific composite scores.
- 5.2.3** To test whether 12 months of aerobic exercise, relative to the control, reduces brain atrophy and increases blood flow in the hippocampus and in prefrontal (superior frontal, caudal-middle frontal, rostral-middle frontal, pars opercularis, pars triangularis) and AD signature (parahippocampus, fusiform, inferior temporal, middle temporal, inferior-parietal) composite regions, measured using volumetric and arterial spin labeling magnetic resonance imaging (MRI).
- 5.2.4** To test whether 12 months of aerobic exercise, relative to the control, favorably alters AD biomarkers in CSF (ab42/ab40, ab42/tau, ab42/p-tau) and blood (ab42/ab40).

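### The 24-hour no-exercise condition does not reach the banked blood draw, so any acute effect of a recent session on blood ab42/ab40 would be confounded with arm

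*Protocol*

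**What the plan says.** Protocol Section 9.5 (Month 12) instructs participants "to refrain from exercise for 24 hours prior to cognitive testing, fMRI (for approved sites), and the LP". Section 12.2.3 repeats the condition for CSF: the Month 12 LP should come "at least 24 hours after the last bout of exercise". At Month 6 (Section 9.4) the instruction is narrower: participants are asked "to refrain from exercise for 24 hours prior to cognitive testing, which should not be completed while participants are fasting". Month 18 (Section 9.6) also ties it to cognitive testing only.

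Banked blood is a separate item at each of these visits; at Month 12 it is listed as "Fasting blood collection for banking". Its collection conditions are in Section 12.2.2: blood is drawn "in the morning after a minimum 10-hour overnight fast". No exercise condition is stated there or in the visit lists. On scheduling at Month 12, Section 9.5 says: "The following procedures may be completed over multiple days, but within a 7-day window".

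The SAP (Section 5.2.4) makes a blood marker a secondary outcome. It tests whether 12 months of aerobic exercise "favorably alters AD biomarkers in CSF (ab42/ab40, ab42/tau, ab42/p-tau) and blood (ab42/ab40"). Section 11.2.2 analyses it by an approach similar to the primary analysis, at an unadjusted 0.05. Blood ab42 and ab40 taken singly are exploratory (SAP Sections 5.3.2 and 11.3.3).

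**The concern.** By holding exercise before cognitive testing, fMRI and LP, the Protocol treats a recent session as something to keep out of those measurements. It does not do so for blood and gives no reason for the difference.

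The aim is the effect of 12 months of training. If one session leaves a short-lived trace in plasma, a draw taken soon after it mixes that trace with the training effect. Randomisation does not balance this, because the trace depends on what each arm is assigned to do. All baseline assessments come before randomisation and the start of exercise (Section 9.3), so baseline blood carries no trace of study exercise. At follow-up the aerobic arm trains at 70-80% HRR and the control arm at or below 35% HRR (Sections 6.3.1 and 6.3.2).

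At stake is the reading of one secondary blood ratio and its two exploratory components. An arm difference could not be attributed to training alone, and it would not be strictly comparable with the CSF ratios, which are protected.

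**Working it through.** **Step 1: coverage, from the visit sections and Section 12.2.**

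| Procedure | Month 6 | Month 12 | Month 18 |
|---|---|---|---|
| Cognitive testing | 24 h condition | 24 h condition | 24 h condition |
| fMRI (approved sites) | not done | 24 h condition | not done |
| LP / CSF (if agreed) | not done | 24 h condition | not done |
| Banked blood | none stated | none stated | none stated |

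**Step 2: can a draw fall on an uncovered day?** At Month 12, yes. Procedures may be spread over several days within 7, LP is only for those who agree, the fMRI condition applies only at approved sites, and nothing ties the draw to a covered day. Months 6 and 18 carry no multi-day wording. A single-day visit there is covered in practice through cognitive testing, so Month 12 is the main exposure.

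**Step 3: would an acute effect be linked to arm?** Yes, if there is one, for the reasons given under the concern: an exercise-free baseline and different session intensity afterwards. Section 6.4 also stresses adherence in the 4 weeks before the Month 6 and Month 12 visits, so recent sessions are to be expected.

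**Step 4: does the SAP deal with it?** No. Section 12 (sensitivity analyses) has nothing on time since the last session. The primary approach averages Months 6 and 12 (Section 11.1). If that is carried over to blood, Month 6 draws enter too.

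**Step 5: size.** The plan has no figure for acute effects on blood or for power on blood markers. Its only related calculation is the primary sample size of 291. That reproduces closely: 4 x (4.1 x (1.960 + 0.842) / 1.5)^2 = 234.6, and 234.6 / 0.8 = 293.2. It has no bearing here.

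For illustration only, let f be the share of aerobic-arm draws affected by a recent session and d the acute shift in SD, with no shift in controls and no true training effect. Then:

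- Bias B = f x d.
- Assumed completers per arm = 300 x 0.8 / 2 = 120, so SE = sqrt(2/120) = 0.129 SD.
- False-positive rate = Phi(B/SE - 1.96) + Phi(-B/SE - 1.96).

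Neither f nor d is in the documents. The value 4/7 = 0.57 assumes four attended sessions a week on separate days unrelated to the visit, and no covered draws. The value 0.25 is a lower assumption.

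| d (SD) | f = 0 | f = 0.25: B, rate | f = 0.57: B, rate |
|---|---|---|---|
| 0 | 0, 5% | 0, 5% | 0, 5% |
| 0.1 | 0, 5% | 0.025, 5% | 0.06, 7% |
| 0.2 | 0, 5% | 0.05, 7% | 0.11, 14% |
| 0.3 | 0, 5% | 0.075, 9% | 0.17, 26% |
| 0.5 | 0, 5% | 0.125, 16% | 0.29, 60% |

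The first row and first column are as compatible with the documents as the last row.

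**The case against.** The strongest reply is that the harm is hypothetical. No passage says that a single session moves blood ab42/ab40, or that a shift lasts to the next morning. A proportional change common to both peptides cancels in the ratio. This stands, and it is why no bias can be claimed, only the absence of protection.

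Second, many draws are probably covered anyway. A fasting draw, a meal and then testing fit into one visit. LP also needs an overnight fast, so blood and CSF can share a morning, and Section 12.2.3 expects most participants to have LPs. A reader might infer that the fasting rules force the draw onto a separate day; they do not. They allow same-day collection without requiring it, so the gap remains but its reach is unknown.

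Third, 4/7 is not a bound. Missed sessions lower it, moving sessions away from held days can change it in either direction, and a session on the previous day may already be 24 hours before the draw.

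Two wider readings are also tempting. One is that the 400 m Walk Test, not ordered after the draw, adds to the problem. Both arms do the same walk at the same visits, so it does not produce the arm-linked difference at issue. The other is that BDNF, VEGF and inflammatory markers in blood are equally exposed. Protocol Aim 6 names them as exploratory, but the SAP lists only ab42/ab40, ab42 and ab40 for blood and places BDNF in CSF.

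Finally, the SAP reports 296 participants enrolled, so a protocol change may affect few or no samples in this trial. That is fair, and it makes the analysis of samples already collected the more useful part of the fix.

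**Conclusion.** The omission is real and plain in the text. It leaves blood ab42/ab40, and the exploratory single peptides, open to confounding between a recent session and assigned arm, mainly at Month 12. The conclusion rests on two conditions that the documents do not settle: that some draws fell within reach of a session, and that a session has an acute effect on these markers that differs by arm. If either fails, the bias is zero. A reader might go further and conclude that the blood result is biased, or that an observed difference would be an artefact; the documents do not support that. The primary, other cognitive and CSF outcomes are not affected, and no sample-size change follows. This is a low-cost improvement to a secondary outcome, not a threat to the trial's main conclusion.

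**What to change.** In Protocol Sections 9.4, 9.5, 9.6 and 12.2.2, add the banked blood draw to the procedures covered by the existing 24-hour condition, or require the draw on a day already covered by it. Record the date and time of the last exercise session with the sample.

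For samples already collected, derive time since last session from the Physical Activity Logs, in which participants enter the date and time of every supervised and unsupervised session (Section 6.3). Tabulate it by arm and visit first; if nearly all draws are at least 24 hours after a session in both arms, the point is closed. Then add to SAP Section 12 a sensitivity analysis of blood ab42/ab40 by time since last session, for instance restricted to draws at 24 hours or more. Label it exploratory: time since last session is a post-randomisation variable, and restricting on it can introduce selection.

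The cost is a line in each of four sections, one field on the sample record, one extra analysis and slightly tighter visit scheduling.
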